8. MANAGEMENT OF THE DATA

The collected data will be managed into a dedicated electronic case report form (CRF). The CRFs will be stored on a dedicated and validated website. Only the Investigators will have access to the data with a personal password. Only the PI and the first data manager will be able to see all the data, while the other investigators will have permission to manage only the data of the patients enrolled in their center.

To ensure the correct data collection two Investigators will perform the clinical and radiological assessment at each follow-up visit. Before the conclusion of the visit, a double-check will be performed by the Investigators. The CRF will be completed at the time of enrollment and each follow-up visit thereafter. The CRF required data are declared below.

A personal code will be generated at the enrollment. The CRF will be filled anonymously. The following anamnestic data: age, sex, comorbidities (hypertension, cardiopathy, hyperlipidemia, peripheral arterial disease, previous surgery, etc). Procedure planning details were detailed previously. The procedure details: planned and unplanned adjunctive procedure, the adverse events, the skin-to-skin time, the fluoroscopy time and DAP, the type of anesthesia, the dose, and characteristics of CM used. Primary and secondary endpoints will be registered as defined previously.

The following indicators will also be collected: time of recovery from the intervention and the number of an hour passed in the Intensive Care Unit if needed.

In case of the patient's voluntary withdrawal, the CRF will be discontinued. The patient will undergo standard clinical practice follow-up.

In case of device-related adverse-events, a detailed description of the event will be performed to inform the regulatory authority. The clinical follow-up and the CRF proceed as stated.

In case of death, the study personnel will investigate the cause and any eventual relation with the treatment or device will be declared to the regulatory authority and carefully reported on the eCRF.

Statistical methods

Continuous variables will be expressed as mean, and standard deviation, and differences tested with the two-sided t-test or the Mann–Whitney U-test, if appropriate. Categorical variables will be expressed as counts and percentages and the chi-square test or Fisher's exact test will be used for analysis. All data will be entered into the logistic regression model if they had a univariable P-value of <0.05 . Data resulting significant in this model will be put in a multivariate one. In the multivariable analyses, clinical factors or potential confounding variables will be expressed as odds ratios with 95% confidence interval (CI). The goodness of fit of the logistic regression models will have been assessed by calculating the C-statistic. Survival analysis and freedom from adverse events will be assessed through the Kaplan-Meier analysis with their relative 95% CI. A P-value < 0.05 defined the statistical significance. The analysis was carried out using STATA 15.1 (StataCorp College Station, Texas, USA).

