Surgical procedure

All the procedure were carried out in a standard operating room equipped with a mobile C-Arm, or in a Hybrid theater under local sedation or general anesthesia on the basis of comorbidity and/or surgeon preference. A bilateral percutaneous access was obtained, even if based on the specific case a cut-down and contralateral percutaneous access is possible. Hemostasis was achieved using the Proglide/Prostyle (Abbott Vascular, Abbott Park, IL, USA) if percutaneous access was used. Intraoperative heparin dosing varied by the center. However, generally, heparin was administered to maintain an activated clotting time > 250 seconds, when possible.

Techniques for delivery and deployment of the standard device have been well described by different papers¹⁰⁻¹², but for the “prototype” some attention is required.

Once the device was advanced at the level of the lowest RA the C-Arm has been moved to correct the parallax effect and positioned orthogonally to the origin of the artery. This procedure permits perfectly matching the scallop with the artery takeoff.

A selective angiogram was performed to assure the patency of the lower RA.

After the deployment of the main body proper iliac extensions were delivered to completely exclude the aneurysm as standard practice.

The complete exclusion of the AAA was checked with a final angiography and then all devices were removed. Heparin was antagonized with the appropriate dose of protamine and access was closed.

According to our standard of care, patients are discharged on the second postoperative day on either aspirin or clopidogrel, if not already on one of these medications.

Follow-up

The first clinical evaluation (before surgery) was performed before discharge primarily to check the femoral access. All the patients will be assessed clinically and with a high-quality CTA (from 6th rib to groin) within 3 months from surgery and yearly for 5 years thereafter for a total of seven evaluations. All the visits will be performed by Investigators.

The patients will be followed up via telephone call to strictly adhere to the present scheme.

A telephone number of the Vascular Surgery Unit will be daily available for any patient's clinical issue during the study period. The clinical and radiological follow-up will continue regularly as a standard practice also in case of patients' voluntary withdrawal.

Endpoints

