Primary endpoint: Clinical effectiveness measured in terms of technical and clinical success.

Technical success was defined as defined on an intent-to-treat basis and requires the successful introduction and deployment of the device in the absence of surgical conversion or mortality, type I or III endoleaks, or graft limb obstruction. A technical success thus implies the following qualifying details: 1. Successful access to the arterial system using a remote site (ie, the femoral, external iliac, common iliac, or brachiocephalic arteries with or without the use of a temporary or permanent prosthetic conduit to access these arteries); 2. successful deployment of the endoluminal graft with secure proximal and distal fixation; 3. absence of either a type I or III endoleak; 4. patent endoluminal graft without significant twist, kinks, or obstruction (>30% luminal stenosis or a pressure gradient >10 mm Hg) by intraoperative measurements; 5 patency of both renal arteries and at least one hypogastric artery. Primary technical success can include the use of additional modular components, stents, angioplasty, and adjunctive surgical procedures. However, if unplanned endovascular or surgical procedures are necessitated it must be noted.

Clinical success requires the successful deployment of the endovascular device at the intended location without death as a result of aneurysm-related treatment, type I or III endoleak, graft infection or thrombosis, aneurysm expansion (diameter >5 mm, or volume >5%), aneurysm rupture, or conversion to open repair, occlusion of the renal arteries. The clinical success was measured at every follow-up interval. Any additional maneuvers, planned or unplanned, aimed to maintain clinical success must be carefully reported.

Secondary endpoints:

- Evaluation of the intra-operative and peri-operative (within 30 days) adverse events

- Collection of eventual adverse events related to the treatment procedure and eventual post-hoc analysis
- Evaluation of reintervention (time elapsed since index operation, type, and indication);
- Evaluation of potential risk factors (baseline, anatomical features, procedural technique) potentially related to adverse events
- Evaluation of the main procedural and fluoroscopy time, evaluation of the average contrast medium (CM) dose as well as Dose Area Product (DAP) (mGym3).

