Adverse events are defined as any systemic or local complication directly related to the procedure. Adverse events that occurred in the first 30-day were considered procedure-related, unless differently demonstrated.

Any surgical, open, or endovascular, procedure aimed to address adverse events was named re-intervention.

The secondary endpoints represent specific technical aspects related to the procedure and the endograft.

Treatment-related adverse events and re-interventions are important to state the safety of the procedure over time and its external reproducibility.

The procedure and fluoroscopy time, as well as the contrast-medium dose, will be used to evaluate the complexity of the procedure, comparing it with the same reported in the literature for standard EVAR.

Timeline

[figure not shown]
Months 1-3 Organization and logistic set-up.

Months 3-15 Subjects enrollment, data collection, treatments, clinical follow-up.

Months 15-18 Conclusion of recruitment, first (3 months) follow-up end for every patient, ad-interim analysis

Month 27-39 2-year follow-up end, mid-term analysis

Month 63-75 Conclusion of the follow-up, analysis of the results and their validation,

statistical analysis, project completion and analysis for further work, dissemination of the results

Gantt chart:

Sample size

No statistical analysis of the sample size was carried out. Considering the number of AAA responding to the inclusion criteria treated in the participating centers and the enrollment period (1 year) a sample size of 50 patients was estimated. This number should be sufficient to evaluate the endpoints reported in the appropriate section.

The estimated number of patients recruited for the present center is 15 patients

Recruitment

All the involved centers represent the third referral level of complex Abdominal Aortic Aneurysms.

For what concerns our center all patients affected by AAA responding criteria for treatment were evaluated at the Vascular Surgery Unit of the Azienda Ospedaliero Universitaria di Modena. Those meeting the inclusion criteria will be singularly recruited.

Taking into account a mean of 120 endovascular procedures on the abdominal aortic and 10 complex procedures with custom-made devices, a safety 12-month recruitment should be considered. The entire Medical staff of the department is informed about the present project and will refer the potential subjects to the Investigators.

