9. MONITORING

The monitoring committee will be composed of Investigators. The PI will supervise the committee. The committee will monthly revise the data until the end of the study. The committee will collectively resolve any issues related to the data collection.

The committee will produce ad interim analyses. Eventual adverse events (mild and/or severe) will be internally investigated by the monitoring committee and externally communicated according to the local regulatory authority disposition. The auditing process will be independent.

The study will be stopped in case of early signs of arm. The PI will decide on the early interruption. The PI will communicate the decision within 15-day as the local regulatory authority advise (DM 21.12.2007). The interruption will be conducted under the local regulatory authority.

The Investigators will diffuse the data even in case of early interruption.

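### No contact is scheduled at day 30 and no deadline is set for entering events between visits, so 30-day adverse events after discharge may be missed, poorly dated or reviewed late

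*Combined protocol and SAP*

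**What the plan says.** **Endpoint and attribution.** The first secondary endpoint in section 7 (Endpoints) is "Evaluation of the intra-operative and peri-operative (within 30 days) adverse events". The same section defines adverse events as complications directly related to the procedure and sets the cut-off for presuming that relation: "Adverse events that occurred in the first 30-day were considered procedure-related, unless differently demonstrated".

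**Contacts.** Under Surgical procedure, "patients are discharged on the second postoperative day". Under Follow-up, "The first clinical evaluation (before surgery) was performed before discharge primarily to check the femoral access". Clinical and CTA assessment then takes place "within 3 months from surgery and yearly for 5 years thereafter for a total of seven evaluations". The inclusion criteria give a different scheme: CTA at 3 months, 12 to 18 months and 5 years, with clinical and duplex examinations at 6, 12 and 36 months and yearly after that. Follow-up also provides for undated telephone calls to support adherence to the scheme, and for a telephone line that patients can ring on any day.

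**Recording.** Section 8 states: "The CRF will be completed at the time of enrollment and each follow-up visit thereafter". It also lists adverse events among the procedure details, has deaths investigated with any relation to treatment or device reported on the eCRF, and requires a description of device-related events for the regulator. Section 5 commits all adverse events to the CRF with prospective monitoring.

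**Review.** Section 9 says of the monitoring committee: "The committee will monthly revise the data until the end of the study". The committee also investigates adverse events internally, and the study may be stopped on early signs of harm.

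**The concern.** A 30-day endpoint needs a point at which someone asks, at or near day 30, what has happened since discharge. Neither visit scheme contains one. The only step before discharge is aimed mainly at the femoral access, and its own sentence places it both ahead of the operation and ahead of discharge.

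Three things are at stake.

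- **Ascertainment.** Non-fatal events after discharge may be recalled incompletely at a later visit. If a patient withdraws first, section 8 discontinues the CRF.
- **Dating.** Both the 30-day count and the presumption of relatedness depend on whether an event fell before or after day 30. The Kaplan-Meier analysis of freedom from adverse events (section 8, Statistical methods) also needs event dates. An endoleak or renal occlusion first seen on a CTA at day 80 has no known onset, and the plan has no rule for it.
- **Timeliness.** Implantation continues while the committee reviews monthly, and no entry deadline ensures that a recent event is in what it reviews. Section 8 lets only the principal investigator and the first data manager see all data. With 15 of the 50 patients expected at the present centre, 50 − 15 = 35 would come from other centres, so prompt entry matters.

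**Working it through.** **Inputs.** Discharge on day 2 and seven evaluations (section 7, Surgical procedure and Follow-up); a 30-day window (section 7, Endpoints); 50 patients over 12 months (section 7, Sample size and Timeline); monthly review (section 9). A first visit at day 90 is the latest reading of the three-month limit.

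**1. Reproduce the visit count.** One evaluation before discharge + one by three months + five yearly = 1 + 1 + 5 = 7. This matches the stated total, so the count leaves no room for a separate 30-day visit. The scheme in the inclusion criteria has none either.

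**2. Part of the window after discharge.** 30 − 2 = 28 days; 28/30 = 93%.

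**3. Delay to the first visit, if at day 90.** An event on day 30 waits 90 − 30 = 60 days. An event on day 2 waits 90 − 2 = 88 days. An earlier first visit is permitted and would shorten both.

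**4. Patients implanted meanwhile.** 50/12 = 4.17 per month at even accrual. Over the three months from one patient's implant to a day-90 visit, 4.17 × 3 = 12.5, or about 12. Counted from the event itself, in 30-day months, the range is 4.17 × 60/30 = 8.3 to 4.17 × 88/30 = 12.2. These are ceilings: they assume that no call, investigation or other report brings the event forward.

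**5. Monthly reviews without new visit data for one patient.** Reviews falling strictly between visits are the gap in months minus one.

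| Scheme | Visit months | Reviews between visits |
|---|---|---|
| Follow-up | 0, 3, 12, 24, 36, 48, 60 | 2, 8, 11, 11, 11, 11 |
| Inclusion criteria | 0, 3, 6, 12, 36, 48, 60 | 2, 2, 5, 23, 11, 11 |

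A CTA at month 18 would cut the 23 to at most 17. These counts apply to each patient. Across the cohort, new forms arrive every month during enrolment.

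**6. Possible under-recording, on assumptions only.** The documents give no event or recall rate. Let p be the true 30-day rate, s the share of events after discharge and r the share of those captured. The expected recorded count is 50 × p × [(1 − s) + s × r]. With s from 0.3 to 0.5 and r from 0.5 to 0.8:

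- p = 0.10: 3.75 to 4.7 recorded, against 5 true.
- p = 0.30: 11.25 to 14.1 recorded, against 15 true.

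This shows only how such a loss would scale. It is not an estimate for this study.

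**The case against.** The plan has more routes for events than its visit schedule suggests, and several stronger readings fail on the text.

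- **That the 30-day endpoint has no collection point.** A reader might infer this, but section 8 puts adverse events in the procedure details and says the endpoints will be registered, and section 5 commits all adverse events to the CRF. In-hospital events can be recorded at once, and events on days 2 to 30 can be recorded at the first visit. What is missing is a dated, timely contact.
- **That the CRF is filled only at visits.** The section 8 sentence does not say so, and deaths and device-related events have their own handling. However, no entry deadline is given for either, and for device-related events the section says the CRF carries on as already stated.
- **That patients have no contact for three months.** Section 7 plans calls and a daily line. The calls have no dates and no event questions. The line depends on the patient, cannot reveal silent events, and has no stated path to the CRF.
- **That the committee works on stale data.** Section 9 has it investigate adverse events, and its members are investigators. The delay is possible for an individual patient between visits; it does not describe the whole database.
- **That silent findings on the first CTA date from the implant.** Nothing in the documents supports this. Section 7 requires a final angiography and a selective lower renal angiogram, and technical success requires absence of type I and III endoleak and patent renal arteries. In a technical success, that imaging already argues against onset at implantation. Such findings also still count against clinical success and can enter the secondary endpoint on treatment-related events, which has no time limit.

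These points narrow the concern. None supplies a day-30 contact or an entry deadline.

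**Conclusion.** The concern holds in limited form. The plan defines a 30-day endpoint and a day-30 attribution rule but fixes no contact between discharge on day 2 and a first visit that may be as late as three months. It also sets no deadline for entering events that arise between visits. Non-fatal events after discharge, over 28 of the 30 days, therefore depend on retrospective capture that may come 60 to 88 days later. They may be missed, imprecisely dated or late for review.

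The figure of about 12 further implants is a worst case. It rests on even accrual, a first visit at day 90 and failure of every other reporting route. A reader might conclude that early harm will be understated by a known amount; the documents give no event or capture rate, so neither the loss nor its size is established. This is a weakness in ascertainment and timing that is cheap to correct before enrolment and cannot be fully repaired afterwards.

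**What to change.** 1. Add a scripted safety call at day 30 (± 7 days) with its own CRF page covering readmission, re-intervention, death, and limb or flank symptoms. It can use the telephone follow-up already planned in section 7.
2. Complete the procedure page at discharge. State a fixed number of days from awareness for entering deaths, conversions, re-interventions, ruptures, renal occlusions and type I or III endoleaks, in place of waiting for the next visit.
3. Report endoleaks, renal or graft occlusions and limb events first detected on the first postoperative CTA as a separate line beside the dated 30-day count, without presuming when they began. A telephone call cannot find silent events, so this line is needed as well as the call.
4. Reconcile the two descriptions of the first evaluation's timing in section 7 (Follow-up), and reconcile the visit scheme there with the one in the inclusion criteria.

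The cost is about 50 calls, one CRF page and some protocol wording. The reported early event rate may rise because more events are found. That should be borne in mind when the results are set against published standard EVAR series.

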7. METHODS

Setting

Patients affected by AAA with an inter-renal distance $\geq 10\text{mm}$ and eligible for EVAR within standard TReO (Terumo Aortic) IFU will be prospectively enrolled at the Unit of Vascular Surgery of the Ospedale Civile di Baggiovara (Azienda Ospedaliero-Universitaria di Modena) and in the participating centers. The Investigators (3 experts Vascular surgeons⁹) will screen the patients for inclusion. Once the patient's eligibility will be stated, informed consent will be collected and the study could take place.

Inclusion criteria:

- Patients affected by infrarenal AAA $\geq 50\text{mm}$
- Treated in election for non-symptomatic AAA
- Anatomy inside Treo (Terumo Aortic) instruction to use (IFU)
- Distance between renal arteries $\geq 10\text{mm}$ on aortic center-lumen-line
- Age ≥ 18
- Patient fit to plead
- Both sex
- Written informed consent
- Treated in the coordinator center or in one of the study's participating centers
- Minimum follow-up requested: 3-months, 12-18 months and 5-years CTA; clinical and DUS examination at 6- and 12- and 36-months after the intervention and yearly thereafter

Exclusion criteria:

- Patients with aortic pathologies different from AAA (aortic ulcers, dissection, pseudo-aneurysm etc)
- Treated in urgent/emergent setting for symptomatic or ruptured AAA
- AAA < 50mm
- Outside TREO (Terumo Aortic) IFU
- With an inter-renal distance measured of the center-lumen-line <10mm
- Age <18
- Unfit to plead
- Refused to sign the informed consent
- Treated outside the coordinator centers or in one of the study's participating center's
- Refusal to adhere to the requested follow-up

Device description

TREO (Terumo Aortic) was described in different papers.¹⁰⁰⁻¹¹ It is a tri-modular device composed of self-expanding nitinol Z-stents sutured to woven polyester graft fabric. The stent-graft has a proximal bare stent with each edge presenting barbs. The second row of barbs is placed at the external surface of the proximal edge of the fabric. The barbs are nitinol, caudally-directed, sealing adjuncts promoting a better fixation.

The Manufacturer allows customization of the standard design. The investigational endograft was ideated with a single renal scallop (10x10-mm and 15x10-mm, height and width,

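### The CRF closes at voluntary withdrawal although routine follow-up goes on, so late clinical failures can be seen in care yet be missing from the primary endpoint

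*Combined protocol and SAP*

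**What the plan says.** - **Endpoint.** Section 7 (Endpoints) makes technical and clinical success the primary endpoint. Clinical success requires, among other things, no type I or III endoleak, no renal artery occlusion and no "aneurysm expansion (diameter >5 mm, or volume >5" per cent). On timing: "The clinical success was measured at every follow-up interval". Section 6 sets follow-up at 5 years or more.
- **Withdrawal.** Section 8: on "voluntary withdrawal, the CRF will be discontinued", and the patient returns to standard follow-up. Section 7 (Follow-up): "The clinical and radiological follow-up will continue regularly as a standard practice also in case of" withdrawal. Section 8 keeps the CRF open for device-related adverse events and has causes of death investigated. It does not say whether either provision applies after withdrawal.
- **Analysis.** Section 8 (Statistical methods) summarises categorical variables as counts and percentages, without naming a denominator. It adds: "Survival analysis and freedom from adverse events will be assessed through the Kaplan-Meier analysis". Section 7 states: "Adverse events are defined as any systemic or local complication directly related to the procedure".
- **Schedules.** The section 7 inclusion criteria give "Minimum follow-up requested: 3-months, 12-18 months and 5-years CTA", with "clinical and DUS examination at 6- and 12- and 36-months after the intervention and yearly thereafter". Section 7 (Follow-up) gives CTA within 3 months and then yearly for 5 years, seven evaluations in all. The Timeline plans a mid-term analysis when 2-year follow-up ends.

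**The concern.** The components of clinical success most likely to appear late are imaging findings, and the centre will usually see them because routine surveillance continues. Closing the CRF at withdrawal discards this information even where the patient would not mind its use. The device-event and death provisions do not clearly fill the gap: an expanding sac found on a routine scan is neither a death nor necessarily a device-related event.

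The study has one arm, so the success rate at each interval is itself the result, and loss cannot cancel between groups. The data are also meant to inform the development of an off-the-shelf device (section 4). If patients who withdraw do worse than those who stay, the reported rate is too high; if they do better, it is too low. Kaplan-Meier does not cure this, because censoring at withdrawal assumes that those who leave have the same later risk as those who stay.

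A second, smaller question is whether the two follow-up schedules leave some patients without a status at the 2-year analysis.

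**Working it through.** **Inputs.** From the documents: N = 50, no comparator, at least 5 years of follow-up, and the two schedules. The sample size was set by feasibility, so there is no planned rate or dropout figure to reproduce. All failure and withdrawal rates below are assumptions.

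**1. Withdrawal with the CRF closed.** W patients withdraw at 1 year. The others have 5-year success of 0.80. Hazards are constant, so S(t) = S(5)^(t/5). Write Sw for the withdrawn and S for the rest; S(1) = 0.8^0.2 = 0.956.

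- Truth = [(50 − W) × 0.80 + W × Sw(5)] / 50
- Kaplan-Meier (expected) = [(50 − W) × S(1) + W × Sw(1)] / 50 × 0.80 / 0.956
- Percentage among those assessed at 5 years = 32/40 (W = 10) or 36/45 (W = 5)
- Unrecorded failures = W × [Sw(1) − Sw(5)]

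| W | 5-year failure risk in withdrawn | Unrecorded failures | Truth | Kaplan-Meier | Among those assessed |
|---|---|---|---|---|---|
| 10 | 40% | 3.0 | 76.0% | 79.1% | 80.0% |
| 10 | 20% (same as the rest) | 1.6 | 80.0% | 80.0% | 80.0% |
| 10 | 10% | 0.8 | 82.0% | 80.4% | 80.0% |
| 5 | 40% | 1.5 | 78.0% | 79.6% | 80.0% |

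Worked row (W = 10, 40%): Sw(1) = 0.6^0.2 = 0.903. Truth = (32 + 6)/50 = 76.0%. Kaplan-Meier = (40 × 0.956 + 10 × 0.903)/50 × 0.80/0.956 = 79.1%. If an absence of recorded failure were read as success, the figure would be 76.0 + 100 × 3.03/50 = 82.1%.

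The error changes sign with the risk among the withdrawn and vanishes when that risk equals the rest.

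**2. What missing assessments leave open.** If 36 of 40 assessed patients are successes and 10 are missing, the full-cohort rate lies between 36/50 = 72% and 46/50 = 92%. The exact 95% CI for 36/40, 76.3% to 97.2%, does not express that uncertainty. For scale, a complete 40/50 has an exact 95% CI of 66.3% to 90.0%.

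**3. The schedules side by side.**

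- CTA: the inclusion criteria give 3 (3 months, 12–18 months, 5 years); the Follow-up text gives 6 (within 3 months, then 5 yearly).
- The seven evaluations are 1 before discharge + 1 within 3 months + 5 yearly. The 6-month visit in the inclusion criteria is not among them.
- A patient meeting only the inclusion-criteria minimum has no assessment between 18 and 36 months, and so no 2-year status.

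Size at 2 years, with S(5) = 0.80 and failures found only at scheduled imaging: true success is S(2) = 0.8^0.4 = 91.5%. The last available imaging would show S(1.5) = 93.5% or S(1) = 95.6%. The excess is 2.1 to 4.2 points, or 1.0 to 2.1 patients of 50. This is an upper limit: symptomatic failures come to light when they occur, and patients followed yearly do have a 2-year assessment.

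**The case against.** **Stopping the CRF respects the patient's wish.** In an observational study built on standard care, data recording may be most of what a patient can withdraw from. The consent form is not available to this review and may already separate kinds of withdrawal. This stands as a limit on the remedy: continued recording must be the patient's choice. It does not justify closing the record when the patient was never asked.

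**A reader might infer that clinical success has no analysis at all.** The documents do not support that. It is a categorical status at each interval, and Statistical methods provides counts and percentages for such variables. Section 5 also treats endoleaks as procedure-related adverse events, so Kaplan-Meier for freedom from adverse events covers part of the composite. What is unstated is the denominator and the handling of missing assessments; expansion without a complication is the component least clearly covered.

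**A reader might infer that 3 CTAs against 6 is a contradiction.** It is not. The inclusion criterion is worded as a minimum, which the yearly scheme satisfies, and telephone calls support adherence to that scheme. The direct mismatch is the 6-month visit. The 2-year gap arises only for a patient who meets the minimum but not the yearly scheme.

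**The loss rates are invented, and the Kaplan-Meier error is small beside the sampling error.** Both are true. The largest Kaplan-Meier error shown is 3.1 points, against a CI of 66.3% to 90.0%. Refusal of follow-up is also an exclusion criterion, which may reduce losses, although it gives no rule for loss after treatment. The counter is that a confidence interval does not correct a systematic error, and this one is cheap to reduce.

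**Conclusion.** The point holds in a limited form. Imaging failures that decide half of the primary endpoint may be seen in care and not recorded once a patient withdraws. If withdrawal is related to outcome, the late success rate can be biased in either direction; if it is not, Kaplan-Meier and the percentage among those assessed are unbiased.

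The real size cannot be known from the plan. Under the assumptions shown, Kaplan-Meier errs by +3.1 to −1.6 points with 10 withdrawals, and by +1.6 points with 5 withdrawals at 40% risk. The percentage among those assessed errs by +4.0 to −2.0 points and by +2.0 points respectively.

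The schedule issue should not be read as part of that two-way bias. It acts one way, through late detection, and mainly concerns interim results, because both schedules include a 5-year CTA. This is a worthwhile, inexpensive improvement; it does not invalidate the study.

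**What to change.** 1. **Withdrawal.** At consent or at withdrawal, offer the option to stop study participation while still allowing routine-care imaging, reintervention and vital status to be entered in the CRF. If the patient refuses, stop as now and count the patient as missing.
2. **Reporting.** Keep clinical success at each interval as section 7 defines it. Report the percentage with its denominator and 95% CI, and give best- and worst-case bounds for missing assessments. Time to first clinical failure, with non-aneurysm death as a competing event, may be added as a supplementary analysis. It should not replace the interval status, because it would make a later-corrected failure permanent and so change the endpoint.
3. **Schedules.** Reconcile the inclusion-criteria schedule with the Follow-up text, including the 6-month visit, and both with the 2-year analysis. State which assessment counts at each analysis time. Which schedule to adopt is for the investigators.

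**Cost.** A change of consent wording if the form does not already cover this, a few sentences in the statistical section, and some extra data entry. No extra patients are needed. Some patients may refuse, and the late success rate may prove less favourable.
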